4.4.3. Development of G2 (improvement of G1)

	CVD patients	BC patients
August 2024 /Sept	Development of G2 Patient will receive information letters of	every 3 months
2025	CVD Patients will continue using the Medical device (see Section 6) and will continue sending these data to Data Intermediary. In case of problems patient can contact the research associate	

4.4.4. Returning patients (for G2 only)

This is applicable only for patients who have participated to the assessment of G1 and are also assessing G2

	CVD patients	BC patients
2 weeks for start G2: Jan 2026	Refresh training of Expert curators and Research associates	
G2 VISIT 1 - on site W1 Day 1	 Upload of all data (starting from scratch) Patient will be called in for outpatient visit by the res Questionnaire to specify user profile (In Redcap, Use Training session for the patient on the prototype - G Patient fills EQ-5D QALY - quality of life questionnaire Research associate complete REDCap Form (in REDC Patient and expert curator curate medical data with 	search associate er Profile FORM) 2 version - by the research associate (2,5h) e through HDI provided app ap, Patient monitoring FORM) for enrolled patients AIDAVA
W1 Day 2-5	 CVD patient use the medical device Patient will use AIDAVA and test its functionalities, ta Expert Curator will curate the data in AIDAVA, on der RA fill the patient monitoring form (in REDCap, Patient) 	ake notes and if necessary, will contact helpdesk mand ent monitoring FORM)

	CVD patients	BC patients
W1 Day 5	 First calculation of SMART risk score by AIDAVA (automatically) and CVD expert (manually). Data collection and entry forms documentation of SMART risk score calculation result and time (in REDCap, Patient monitoring FORM) 	 System extracts the patient data for insertion into the local AIDAVA BC registry Queries identified as secondary end points will be fired automatically by the system and results available for display to the BC data users
	 AIDAVA extract IPS and forward it automatically to th Data curators spreadsheet (Patient as curator and E Form) Data user/consumers spreadsheet (In REDCap, Data 	ne HDI (+ enter flag in REDCap, Patient monitoring Form) Expert Curator). (in REDCap, Patient Curator FORM; Expert Data Curator user/consumer Form)
VISIT 2 - online W2 Day 1	CVD patients use medical device Check if there is any issue with the medical device (CVD patient only)	
	 Second training session on the prototype - online (open questions) Patient and expert curator curate medical data using AIDAVA RA fill the patient monitoring form (in REDCap, Patient monitoring Form) 	
W2	CVD patient use the medical device	
	 Patient will use AIDAVA and test its functionalities, ta Expert curator will curate the data in AIDAVA on den RA fill the patient monitoring form (in REDCap, Patie) 	ake notes and if necessary, will contact helpdesk nand. nt monitoring Form)
VISIT 3 W2 Day 5 March 2026	 Second calculation of SMART risk score by AIDAVA and CVD expert Data collection and entry forms: documentation of SMART risk score calculation result and time 	 Queries identified as secondary end points will be fired automatically by the system
	 AIDAVA extract IPS and forward it automatically to the HDI (+ enter flag in REDCap, Patient monitoring Form) Data curators spreadsheet (Patient as curator and Expert Curator). (In REDCap, Patient Curator FORM; Expert Data Curator Form) Data user/consumers spreadsheet (In REDCap, Data user/consumer form) Patient and curator will fill in an System Usability Scale online (in REDCap, System Usability Scale - SUS Form) RA fill the patient monitoring form (in REDCap, Patient monitoring Form) 	

	CVD patients	BC patients
	6. End of study	
End of evaluation	Delete personal patient data and PHKG (after finalisatior	of evaluation report)
VISIT 4 - online W4	Feedback to patient	

4.2. End-of-Study

The end of the study is defined as the date of Week 2/ Day 5 in Generation 2, for the last participant in the study. A participant is considered to have completed the study if the participant has completed all periods of the study including the last scheduled procedure shown in the SoA in Section 1.3.

At the end of the study, the final report with consolidated metrics and statistical analysis will be issued.

The personal data that have been curated and generated in the form of Personal Health Knowledge Graph (PHKG) will be maintained within the AIDAVA instance in the hospital up to the end of the project.

At the end of the project, the patients will be asked if they want to keep their PHKG, and if yes where; the data will be transferred to the requested data store. If the patients do not wish to keep the PHKG, a confirmation will be requested to the patient ; in case of confirmation the PHKG will be deleted.

5. Study Population

5.1. Overview

For testing the 2 generations of the AIDAVA prototype, we focused on **2 Therapeutic Areas (TAs) in 3** countries/languages, within **2 types of healthcare organisations.**

We wanted to evaluate 2 different **TAs** to cover a broader scope of type of data collected in these 2 different medical conditions, while limiting the workload for training AI tools. Considering that we want to solve a technical problem that is critical to solve medical issues, we used the following criteria to select the Therapeutic Areas (TAs): 1) clinical areas in need of further clinical research and of high quality, FAIR data; 2) population prevalence that includes a wide potential base of AIDAVA users; 3) patient cohorts and/or registries are available via clinical and HDI partners in the AIDAVA consortium, providing real-life examples of the problems we want to solve. This led us to the selection of the following TAs.

- Breast cancer. Half of breast cancer patients are younger than 64 years. They present an interesting population in the context of AIDAVA, in that they and their loved ones may be highly motivated to do curation tasks and will have sufficient computer literacy to interact with data. While there is no EU-wide breast cancer registry¹⁵; screening registry exists at national level and would benefit from more detailed information¹⁶ and consolidation at EU level. The 3 academic hospitals in the AIDAVA consortium have operational breast cancer registries and/or a large number of patients.
- Cardiovascular disease, specifically for patients at risk of myocardial infarction. Cardiac arrest is 3 times more frequent in 50+ years elderly males than in females; they constitute a nice counterbalance to the females' population in breast cancer. In addition, this is a TA where availability of a high quality personal longitudinal record is extremely valuable for clinical practitioners to predict the cardiovascular risks. All 3 participating centres have a wide cohort of CVD patients.

We focused on 3 **languages** (Estonia/Estonian, Austria/German and The Netherlands/Dutch) as we needed to limit the workload related to annotating text-based documents, required as training sets for the AI algorithms while providing a foundation for demonstrating the approach and showcasing its potential expansion across all EU languages.

In terms of **organisation**, we work with academic hospitals and personal Health Data Intermediaries (HDIs) supporting personal health data sharing on behalf of each consenting patient, and regulated under the emerging European Data Governance Act (DGA). MIDATA and DIGI.me are partners of the AIDAVA project and contributed to the development of the prototype

Country	Academic hospital	Health Data Intermediary
Estonia	North Estonia Medical Center (NEMC)	MIDATA (MID)
Austria	Medical University Graz (Graz)	MIDATA (MID)
The	(CVD) Maastricht University Medical Center (MUMC)	DIGI.me (DME) - certified
Netherlands	(BC) Maastro Clinic (Maastro) MedMij	

¹⁵ https://www.karger.com/Article/Fulltext/503715

¹⁶ https://bmcpublichealth.biomedcentral.com/articles/10.1186/s12889-019-6846-6

5.2 Study Population

The study participants include

- Patients who met the inclusion/exclusion criteria specified below
- **Expert data curators,** i.e. staff from the hospital, responsible for the maintenance of the local AIDAVA registry, extracting data from the patient medical record and inserting them into the registry
- **Breast Cancer specialists**: staff from the hospital responsible for treating patients and active in clinical research with the local breast cancer registry.
- **CVD practitioners:** staff from the hospital responsible for treating CVD patients

The staff from the hospital that will collaborate on the study is specified in Section 10.4.

Inclusion criteria (MUST)	 Data available in EHR within related medical centre Owner and user of a smartphone Consent to give access to their personal data (based on scope provided in the Informed Consent Form) to the data curator identified in the hospital Agree to sign a collaboration agreement with the relevant HDI - for the duration of the study Agree to test the AIDAVA prototype (G1 and G2) and to delegate to a representative data curator in case of issues
Inclusion criteria for BC patients (MUST)	 Gender: All History of a confirmed diagnosis of breast cancer treated with surgery and radiotherapy
Inclusion criteria for CVD patients	Gender: AllConfirmed diagnosis of symptomatic type 1 acute Myocardial Infarction
Inclusion criteria (NICE TO HAVE)	Health and digital literacy
Exclusion criteria	 Data not accessible (for instance for technical reason) Vulnerable persons Children/minors Inability/unwillingness to use smartphone applications Does not use a smartphone Russian only as a language (in Estonia)

The patients will be selected based on the following inclusion/exclusion criteria.

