3.1. Primary endpoints

The **primary objective** of the assessment study is to compare the acceptance and the performance of the AIDAVA prototype versus existing practice, and between the 2 versions of the prototype. To this end, we propose to measure the following endpoints that will be recorded across sites.

Objective	Primary Endpoints
Metric 1. Evaluate acceptance by end users	Metric definition: Structured questionnaire (adapted from a System Usability Scale with additional questions such as I would recommend AIDAVA to my friend, colleague, or family member I am interested / ready to work with AIDAVA when available on the market I understand the purpose of data curation I am ready to spend the needed time to ensure proper data curation The curation process was perfect/acceptable/too long for me Measurement score (M1) through structured questionnaire (System Usability Scale - form) provided in REDCap
Metric 2. Measure	Metric definition
impact on workload for quality enhancement of data (including quality of the different curation tools)	 Compare time spent in curating data in G0 (current situation) G1 (generation 1 of the prototype) G2 (generation 2 of the prototype). Check the amount of data curated in the average time: are there more data being curated together with the ones needed to support the use case
	 Measurement For estimated time spent in curating (M2.1) User entry in dedicated "Curator form" (RedCap) For curators, when requesting an estimate for G0, it is important to ensure that curated data set have the same level of complexity as for G1 and G2 complexity: Extract a sample (synthetic data ?) to be curated including several data sources; Request existing registry stewards to provide a time to curate data up to insertion into registry (M2.2) System check "active" time of user to answer a query Amount of additional data elements are curated automatically computed (M2.3) How many data elements have been curated automatically by the systems (M2.4) How many data elements have required human interventions and been successful answered by the patients (i.e. answer provided to the question)

Objective	Primary Endpoints
	 (M2.5) How many data elements have required human interventions can not be answered by the patients and are sent to the curators (M2.6) How many data elements send to the curators did not get appropriate answer to finish the curation process

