- Procedures conducted as part of the participant's routine clinical management and obtained before signing of the ICF may be utilised for screening or baseline purposes provided the procedures met the protocol-specified criteria and were performed within the timeframe defined in the SoA.
- In the event of a significant study-continuity issue (eg, caused by a pandemic), alternate strategies for participant visits, assessments, medical device distribution and monitoring may be implemented by the investigator, as per local health authority/ethics requirements.

The study is using already collected data, except for personal apps and data collected through the medical devices.

Adverse Events (AEs) or Serious Adverse Events (SAEs) related to the AIDAVA prototype are not expected during this assessment study, as this is a Class 1 medical device supporting patients in managing and curating available data and there are no medical interventions during the assessment apart from collecting additional data.

For CVD patients, in case of medical device deficiency for the CVD use case, the potential risk is that a SMART risk score will not be properly computed. Physicians will calculate the score as well manually and can compare the calculations with the score that AIDAVA has provided; in any case no medical decisions will not be made based on AIDAVA score alone.

In case of a high SMART risk score detected during the assessment, the treating physician should use measures that include promoting a healthy lifestyle through behaviour changes, including nutrition, physical activity, relaxation training, weight management and smoking cessation programmes for resistant smokers. These would ideally help cope with the illness and improve adherence and cardiovascular outcome.

9. Statistical Considerations

The analysis and reporting will be done on all data from all participants at 3 points in time: before the evaluation starts (curator arm only for G0), after G1 evaluation (G1 report) and after G2 evaluation (G2 report).

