9.2 Analysis Sets

Primary endpoint components

The analysis set will include all expert curators and patient participants and will take into account the primary data points (PDP) identified in yellow in the figure below across the 3 arms.

Primary Data Point	Generation	Arm	Description of measures (through RedCap Form and computed)		
PDP1	G0		M2.1 : Estimated time spent in curation per patient record (min)		
PDP2	G1	Expert Curator	M1: System Usability Score M2.1: Estimated time spent in curation per patient record (min)		
PDP3	G2		Same than for G1 - measured for G2		
PDP4	G1	G1 AND G2 users	 M1: System Usability Score M2: Time spent in for curation in min Estimated time in RedCap form (M2.1) Computed "active" time to answer queries (M2.2) Computed amount of data elements curated automatically by system (M2.3) requiring human intervention with answer from the patient (M2.4) 		

Primary Data Point	Generation	Arm	Description of measures (through RedCap Form and computed)
			 without answer the patient and requiring curator input (M2.5) without answer requested from curator but not successful (M2.6)
			M3: Computed data quality scores of curated record in terms of completeness, correctness, consistency and trustworthiness (as detailed in Task 4.6).
			 M4: Computed quality of the NLP concept extraction against the manually annotated data ("gold standard") Precision (M4.1) which measures the fraction of gold standard instances among the retrieved instances Recall (M4.2) which measures the fraction of the gold standard concepts that could successfully be retrieved
PDP5	G2		Same than PDP4 - for G2
PDP6	G1	G1 OR G2	Same than PDP4 - for G1
PDP7	G2	users	Same than PDP5 - for G2

Secondary endpoints

The analysis set will include all data users (BC specialists and CVD experts) and will take into account the secondary data points (SDP) identified in orange in the figure below across the patient arms. As indeed this is about reuse of data, after the curation process; there is no effect expected from the fact that patients did use G1 before G2 or not.

Secondary Data Point	Generation	Arm	Description of measures (through RedCap Form and computed)		
			Breast Cancer		

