9.3 Statistical Analyses

Three tests have be retained

- **Paired t-test**: statistical test that compares the means of two related groups, where each subject is measured at two different time points or under two different conditions. It is used to determine if there is a significant difference between the two groups.
- Mann-Whitney U test (unpaired t-test): non-parametric statistical test used to compare the medians of two independent groups. It is often used when the data are not normally distributed or when the sample sizes are small.
- Wilcoxon signed-rank test: non-parametric statistical hypothesis test used to compare two populations with two matched samples.

Primary Endpoint(s) Analysis

The endpoints are defined in Section 9.2 will be used to support the analysis

Computed	Description of measures	Test & meaning (per H1)			
	Population: Expert Curators				
E1	Difference between data points 1 and 2: E1.M2.1△ = M2.1@PDP1 - M2.1@PDP2 E1.M2.2△ = M2.2@PDP1 - M2.2@PDP2	Paired t-test H1: less time spent in curation in G1 than in G0 for expert curators			
E2	Difference between data points 2 and 3: E2.M1-Δ = M1@PDP2 - M1@PDP3	Paired t-test H1: G2 is more usable than G1 for expert curators			
	E2.M2.1∆ = M2.1@PDP2 - M2.1@PDP3 E2.M2.2∆ = M2.2@PDP2 - M2.2@PDP3	H1: less time spent in curation in G2 than in G1 for expert curators			
	Population:	Patients			
P1	Difference in data points 4 and 5 (i.e. difference between G1 and G2 for arm where patients used G1 AND G2)	Paired t-test (effect of system + training/experience from G1)			
	P1.M1- = M1@PDP4 - M1@PDP5	H1: G2 more usable than G1			
	P1.M2.x∆ = M2.x@PDP4 - M2.x@PDP5	H1: G2 requires less time for curation than G1 H1: G2 enables curation with less human intervention than G1			
	P1.M3-∆ = M3@PDP4 - M3@PDP5	H1: G2 provide same or higher quality than G1			
P2	Difference in data points 6 and 7 (i.e. difference between G1 and G2 for arm where patients used G1 OR G2)	Unpaired t-test (effect of system only)			
	P2.M1- = M1@PDP6 - M1@PDP7	H1: G2 more usable than G1			
	P2.M2.x∆ = M2.x@PDP6 - M2.x@PDP7	H1: G2 requires less time for curation than G1 H1: G2 enable curation with less human intervention than G1			
	Ρ2.Μ3-Δ = M3@PDP6 - M3@PDP7	H1: G2 provide same or higher quality than G1			

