2. For me it is important to know, who has curated my health data and which tools have been used during the curation	Э	Strongly disagree	Strongly agree	
process.	>	Change the slider	above to set a response	
				reset
In my opinion, information regarding this aspect is sufficient in	θ	Strongly disagree	Strongly agree	
* must provide value	$\overline{\varphi}$	Change the slider	above to set a response	
				reset
3. For me it is important to know, whether a health data	Э	Strongly disagree	Strongly agree	
* must provide value	>	Change the slider	above to set a response	
				reset
In my opinion, information regarding this aspect is sufficient in	θ	Strongly disagree	Strongly agree	
In my opinion, information regarding this aspect is sufficient in AIDAVA. * must provide value	H	Strongly disagree	Strongly agree above to set a response	

AIDAVA specific questions				
1 I would recommend AIDAVA to my friend colleague or family	e P	Strongly disagree	Strongly agree	
member.		Change the slider abo	ove to set a response	reset
2. Lam ready to work with AIDAVA when available on the) P	Strongly disagree	Strongly agree	
market.		Change the slider above to set a response		reset
	Ē	Strongly disagree	Strongly agree	
3. I understand the purpose of data curation.		Change the slider above to set a response		reset
4. I am ready to spend the needed time to ensure proper data curation of my data.		Strongly disagree	Strongly agree	
		Change the slider abo	ove to set a response	reset
5. This system is unique and different from anything else	Ð (þ	Strongly disagree	Strongly agree	
available.		Change the slider abo	ove to set a response	reset
6. This system will allow me to manage my health records	E (Strongly disagree	Strongly agree	
better.		Change the slider abo	ove to set a response	reset
Please write down any suggestions you might have on how we could improve/ make AIDAVA easier to use.	θ			
	\bigcirc			
				Expand

Expert Data curators Form

Form to be used by the expert curator to enter performance metrics needed to assess the AIDAVA prototype in G1 and G2.

Expert Data Curator Form - G1 & G2					
Generation of the prototype		8 Q	O Generation 1 O Generation 2		reset
Site name:) (O NEMC - Sihtasu O UM - Maastrich O MUG - Medizini	tus Põhja-Eesti Regionaalhai t University sche Universität Graz	igla reset
Expert Curator ID / pseudonym:		~			
Number of patients supported:		(example:	0 or 12)		
Period of time during which patient rec	ords were supported				
Start:			Today Y-M	-D	

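### The G0 curator time is tied to a registry that only breast cancer is shown to have, and Form 10 does not split G1 time by use case, so E1 can mix tool effect with use-case differences

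*Protocol*

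**What the plan says.** **G0 measurement.** Section 3.1, Metric 2, gives this instruction for current-practice time: "Request existing registry stewards to provide a time to curate data up to insertion into registry". It adds a comparability condition: "it is important to ensure that curated data set have the same level of complexity as for G1 and G2 complexity". The suggested means is a sample covering several data sources, with synthetic data marked by a question mark. Section 9.2 defines the G0 data point PDP1 as "M2.1 : Estimated time spent in curation per patient record (min"), and PDP2 (G1) uses the same unit. Neither names a use case.

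**Who the curators are.** Section 5.2 describes them as hospital staff "responsible for the maintenance of the local AIDAVA registry, extracting data from the patient medical record and inserting them into the registry". Section 4.1 plans three per site, alongside 15 BC and 15 cardiac patients.

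**Which registries exist.** Section 5.1 says of breast cancer that the hospitals "have operational breast cancer registries and/or a large number of patients". For cardiovascular disease it mentions only a wide patient cohort. Section 2.2 sends BC curation to a registry extract and cardiac curation to the SMART risk score. Section 3.2.2 describes manual SMART scoring as work of the treating physician.

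**G1 measurement.** Section 4.4.2 has the expert curator working on demand. Form 10 (Section 10.3.3) asks for "Number of patients supported" and weekly hours summed to one total. It has no therapeutic-area item; the patient curator form (Form 11) has one.

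**Test.** E1 in Section 9.3 is a paired t-test of PDP1 minus PDP2 over all expert curators: "H1: less time spent in curation in G1 than in G0 for expert curators".

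**The concern.** Section 9.1 states the primary objective as superiority of G1 over the current situation and names time (M2) and quality (M3) as the two critical metrics. M3 is computed only at G1 and G2, and the opening of Section 9 limits G0 reporting to the curator arm. The claim against current practice therefore rests on E1.

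If the G0 time refers to BC records and the G1 time to a mixture of BC and cardiac records, the paired difference holds two things: what the tool changed, and how far a cardiac record differs in effort from a BC record. Pairing within curator removes differences between people. It does not remove a change in the kind of record between the two occasions.

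The gap cannot be repaired later. G0 is collected in one week before G1 is deployed (Section 4.1). If no cardiac G0 time is taken, and G1 hours are not recorded by area, no analysis can reconstruct the split.

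**Working it through.** The protocol gives no effect size, standard deviation or power for E1, so there is no figure of its own to reproduce.

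**1. Which tests use a G0 point.** Among the primary contrasts in Section 9.3, E1 uses PDP1. E2, P1, P2, A3 and A4 compare G1 with G2 or one arm with the other, and A1 and A2 are descriptive. Section 3.1 mentions a G0 count for M4, but Section 9.2 gives it no data point and Section 9.3 no test. U0 uses G0 but is secondary and BC only. E1 is therefore the only primary test against current practice.

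**2. Shift with no tool effect.** Let tB and tC be the curation times for a BC and a cardiac record, r = tC/tB, and s the cardiac share of the records supported at G1. Suppose G0 is measured on BC records.

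- G0 = tB
- G1 = (1 − s)·tB + s·r·tB
- apparent saving as a fraction of tB = (G0 − G1)/tB = s·(1 − r)

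Planned enrolment (15 and 15 per site) suggests s = 0.5. The ratio r is not in the documents, so a range is shown:

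| r | 0.5 | 0.75 | 1 | 1.25 | 1.5 |
|---|---|---|---|---|---|
| apparent saving | +25% | +12.5% | 0 | −12.5% | −25% |

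**3. What that does to the test.** Assume a two-sided 5% paired t-test with every curator having the same mix. The noncentrality is (shift/SD)·√n. Section 9.4 gives 12 curators in the text and 9 in the table, so both are shown. The SD of the paired differences is assumed.

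| shift | SD (share of tB) | P(reject), n = 9 | n = 12 |
|---|---|---|---|
| 25% | 25% | 0.75 | 0.88 |
| 25% | 40% | 0.38 | 0.51 |
| 12.5% | 25% | 0.26 | 0.35 |
| 12.5% | 40% | 0.13 | 0.17 |

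The rate with no use-case difference is 0.05.

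**4. If curators are assigned by area.** A BC curator then has zero shift. A cardiac curator has the full 1 − r if given a BC baseline, or no G0 value if no cardiac task is set. With one or two of three curators per site cardiac and r = 0.5, the mean shift under a BC baseline is (1/3)(0.5) = 16.7% or (2/3)(0.5) = 33.3%. If they give no G0 value, E1 becomes a BC comparison while still being worded for all expert curators.

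**5. After the change.** Within one use case s = 0, or equivalently tC = tB. The shift is 0 and the rejection rate returns to 5%.

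**The case against.** Several points weigh against this.

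- **The formal definition is neutral.** PDP1 and PDP2 are both curation minutes per patient record, and Section 5.2 describes a job, not a measurement. A reader might infer from Section 5.2 that G0 is defined as the time to insert a record into a registry. It is not: Section 3.1 asks for time to curate up to insertion, which is the whole curation task. But Section 3.1 is the only operational instruction for G0, and it is tied to a registry.
- **Cardiac curation may already exist.** Section 2.3 mentions data sets for a registry or a clinical care score as curator work, and nowhere does the protocol say that there is no cardiac registry. Its absence is inferred from silence. What stands is that no cardiac G0 task is defined.
- **Curator IDs carry BC or CV codes** (Sections 10.3.2 and 10.3.3), so pooling within one person is not established. But the protocol does not say that a curator serves one area only, and the case of a split by area is not clean either (step 4).
- **Complexity matching is required.** This targets the problem, but no method is fixed and use-case mix is not mentioned. It reduces the risk without removing it.
- **Form 9, the G0 curator form, is listed but its content is not visible here.** It may separate use cases. Form 10 would still not.
- **Within-use-case estimation can be left to a statistical analysis plan.** That holds for the analysis, not for data that must be collected at G0 and on Form 10.

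**Conclusion.** The point stands as a risk to the interpretation of E1, not as a demonstrated bias. As written, E1 can mix tool effect with use-case differences, because the G0 task is set in registry terms, no cardiac counterpart is defined, and Form 10 does not record time by area. The range from a 25% saving to a 25% loss is illustrative. It assumes no tool effect, G0 on BC records, half the G1 records cardiac, and a time ratio between 0.5 and 1.5.

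Two stronger readings are not supported.

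- A reader might count about 84 registry data elements in Section 10.5 against about 15 SMART inputs in Section 3.2.2, a ratio of 15/84 = 0.18, and infer a spurious saving of 0.5 × (1 − 0.18) = 41%. That assumes time scales with the output elements. Yet the tool curates the whole ingested record, and Section 10.1 marks 12 source types for BC and 13 for cardiac. On that count r = 13/12 = 1.08 and the shift is about a 4% loss, the opposite sign. Neither proxy settles the matter.
- A reader might extend the point to E2. Sections 4.1 and 9.4 plan the same numbers per use case, with the same task at both generations, so the documents give no reason to expect a change of mix.

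A separate mismatch remains: G0 asks for complete curation while G1 curator work is on demand. E1 could show a saving for that reason even with identical case mix. Its size cannot be derived either.

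**What to change.** - In Section 3.1 and PDP1, take the G0 time from each curator separately for a BC record (up to registry insertion) and for a cardiac record (up to the SMART data elements). Check that Form 9 has both entries.
- Add therapeutic area to Form 10, as on Form 11, with hours and number of records per area.
- Compute E1 within use case.
- Where a site has no current cardiac curation, say so and limit the E1 claim to breast cancer.

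The cost is one form item, one further G0 entry per curator and a change of wording. The price in inference is fewer curators per comparison, if curators turn out to work in one area only, and possibly a narrower claim against current practice. The G0 entry must be in place before the one-week G0 epoch and the form item before G1 starts.
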